Enrollment and Study Implementation. Study staff will explain the study to veterans and, if interested, the consent form and a one page project description will be mailed. Appointments will then be made for three days of evaluation. Day 1: informed consent; cognitive, psychological and functional screening; Day 2: neuropsychological and self-report measures; and Day 3: cardiopulmonary testing and biological measures. When these evaluations are completed, eligible participants will be scheduled for the first exercise session within two weeks. The exercise training portion of intervention is approximately 24 weeks. After completion of the exercise training, participants will be re-assessed with the cardiopulmonary exercise testing, cognitive measures, biological measures, outcome measures, and measures of physical activity. Participants will then begin four weeks of thrice weekly cognitive training classes at VAPAHCS. At completion of the cognitive training, participants will undergo the post-treatment assessment: cardiopulmonary exercise testing, cognitive measures, biological measures, outcome measures, and measures of physical activity. Participants will receive payments of \$50 for each set of assessments completed.

We plan to telephone screen 200 participants, based upon prior work (Myers et al., 2010; Yesavage et al. 2008), half or 100 are expected to proceed to an in-office evaluation (10 per month), half, or approximately 50 enrolled (5 per month). Dropouts will not be replaced as this is a feasibility study and an aim is to evaluate the appropriateness of the inclusion and exclusion criteria.

All in-house exercise sessions and activity surveillance will be supervised by exercise physiologists certified by the American College of Sports Medicine (ACSM). CT will be taught by the PI.

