**Measures**: There are three primary time points (Time 1: Screening/Baseline, Time 2: End of Exercise Training, Time 3: End of CT) at which participants will complete cognitive, psychological, physiological, and biological assessments. Screening measures include measures of episodic memory (Logical Memory I and II from WMS-IV; Wechsler, 2008), mental health (MINI; Sheehan et al., 2002), activities of daily living (Functional Activities Questionnaire (FAQ); Pfeiffer, 1982), a semi-structured interview of cognitive impairment (Clinical Dementia Rating Scale (CDR); Morris, 1993), and assessment of risk factors for vascular dementia (modified Hachinski; Rosen et al., 1980). Measures collected during the cardiopulmonary exercise testing include the VA Prognostic Score, and Veterans Specific Activity Questionnaire (VSAQ; Myers et al., 1994), all of which will be used to estimate risk and assess suitability for exercise training (Gibbons et al., 2002; Morrow et al., 1993). The VSAQ will be used specifically to estimate exercise capacity and thus individualize the intensity during the cardiopulmonary exercise test. Veterans who are not eligible to participate because of cognitive, psychiatric, or medical issues will be referred for further diagnostic work-up or treatment to the Memory Disorders Clinic at VAPAHCs, which provides diagnostic services to older veterans. **Data collected regarding the reasons for exclusion will be analyzed to provide support for the appropriateness of the inclusion and exclusion criteria**. **Feasibility** will be assessed through examination of recruitment and retention rates. **Participant adherence**: Participants will wear heart rate monitors during exercise sessions and pedometers throughout the exercise phase of treatment. They will also log their activities on a 7-day activity recall questionnaire. Data from the pedometers, heart rate monitors and the 7-day activity recall will be collected from participants when they return for the VAPAHCs-based exercise sessions. During CT, participants will have homework and complete quizzes assessing their knowledge of the techniques. They will also complete logs tracking their use of mnemonic techniques. These quizzes and logs of homework completed will serve as measures of participant adherence during the cognitive training portion of the study. The **proposed primary outcome measure** is measure of delayed recall on a 16-item Word-List Task. Equivalent alternate lists of words will be used to counterbalance across time points. The **proposed secondary outcome measure** is recall of a 12-item Name-Face Pair Task. Both the Word-List Task and the Name-Face Pair Task have been used successfully in our prior research and have been shown to be sensitive to the mnemonics taught in the CT (i.e., Method of Loci and Name-Face Mnemonic) (Yesavage et al., 2008). **Cognitive measures** include measures of verbal learning and memory (Rey Auditory-Verbal Learning Test; Lezak, 2004), working memory (Digit Span from WAIS-IV; 2008), processing speed (Symbol Digit Modalities Test; Smith, 1991); attention (Stroop Color and Word Test; Golden 1978), and subjective memory impairment (Multifactorial Memory Questionnaire; Troyer and Rich, 2002). Self-report **measures of physical activity** include the Yale Physical Activity Survey (DiPietro et al., 1993). Finally, **biological measures** will be collected from participants. These include measures of DNA, which will be collected through blood collected at VAPAHCs. We will examine both APOE and BDNF genotypes. The APOE genotyping will be performed according to the restriction isotyping protocol of Hixson and Vernier (1990). BDNF genotyping will also be conducted in-house by [name] staff. Additionally, plasma concentrations of BDNF will be measured using

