### **Database Management and Planned Statistical Analyses**

Data Collection and Database Management. There are three proposed testing time points in this study: prior to randomization (T1), at the end of the exercise program and prior to beginning CT (T2), and at the end of the CT (T3). All identifying information will be removed as data are coded by a unique subject number/identifier. Only the PI and her designee will have access to the identifying information linking subject number to name. All data will be checked for completeness and every effort made to obtain missing data. Data storage will be on computerized password protected databases that are backed up nightly. Additionally, our MIRECC and associated laboratories are familiar with the relevant security and confidentiality issues pertaining to genetic materials and take extra safeguards to protect this information.

Data Analyses. Descriptive analyses of categorical variables will include frequency tables; we will compute measures of central tendency (mean, median, standard deviation, and interquartile range) for those continuous variables. Additionally we will examine the distribution of scores on dependent measures to test assumptions of normality and homogeneity of variance and thus make appropriate transformations when necessary.

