Specific Aim 1: WATER+CT will be feasible as shown by good recruitment and retention rates. Statistical Analyses: To test feasibility of the proposed project, the ratio of enrolled to completed participants will be calculated;  $\geq 80\%$  will be considered good retention. Specific Aim 2: To evaluate the appropriateness of suggested inclusion and exclusion criteria for the aims of the proposed project. Statistical Analyses: We will examine the reported adverse events for participants as well as reasons for screening failures (i.e., those who are consented but excluded from participation prior to randomization). Descriptive analyses of these data will include frequency tables and be used to provide justification for the proposed inclusion and exclusion criteria or to modify them appropriately. Specific Aim 3: To evaluate appropriateness of the WATER+CT for study goals. Statistical Analyses: Appropriateness of treatment conditions will be determined through examination of the participant adherence data. Adherence data will include information from pedometers, heart rate monitors, 7-day activity logs, and cognitive training homework logs. Adequate adherence to exercise prescriptions and CT homework will be defined as completion of  $\geq 80\%$  of assignments as defined by self-report and trainer observation. Specific Aim 4: To assess outcome measurement techniques for participant rate of response in WATER+CT. Statistical Analyses: As this is a single-arm trial, a direct comparison between the WATER + CT condition and a comparative condition is not possible. Participants response rate will be determined by examining the percentage of participants who evidence clinically relevant change after study participation. To determine what a clinically relevant difference in the primary outcome measure (delayed recall of a Word List) would be, we reanalyzed data from our initial clinical trial (Yesavage et al., 2008). Our strategy was to look in that study at the difference in baseline scores between 60 year olds and 70 year olds on the same measure as the proposed work. We found that the difference was 1.7 words. We believe that showing such a difference would be clinically meaningful insofar as it represents a decade of aging's effects on memory. This will be an intent-to-treat analysis, thus all data will be analyzed. Specific Aim 5: To examine outcome "moderator" and "mediator" measurement techniques to determine: a) in whom and under what conditions clinically relevant change occurs and b) the mechanisms through which clinically relevant change occurs. Here we are referring to within subjects effects. Statistical Analyses: Multiple regression modeling will be performed in a preliminary manner to examine individual differences in treatment response depending on baseline (T1) characteristics (age, level of education, APOE and BDNF genotypes). A significant Response Rate X Moderator interaction indicates a differential response rate, e.g., the response rate depends upon age. Such measures are "moderator" variables, i.e., they are used to determine on whom or under what conditions improvement occurs. Additional analyses will be performed to examine the extent to which individual differences in the efficacy of CT treatments depend upon changes in cardiovascular functioning, BDNF plasma levels, and changes in efficiency of working memory (Digit Span) during combined aerobic and resistance exercise training (T1 to T3). These analyses use changes in these two measures as "mediator" variables, i.e., they are used to determine how or why improvement occurs.

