Study Procedures. Once recruited and successfully screened (i.e., Time 1 assessments), participants will meet with the study staff to develop an exercise prescription based upon the information obtained during the screening process. For the first two months of the exercise training, participants will attend thrice weekly exercise sessions at the VAPAHCs Aquatic Therapy Center. These training sessions will feature a combination of land-based stretching and water-based exercises to achieve the targeted cardiovascular training zone. *All pool-based exercise sessions will include five-minute warm-up and cool-down sessions prior to and following a combination of land-based stretching and water-based exercises to achieve the targeted cardiovascular training zone. These aquatic exercises will incorporate resistance training, functional exercise movements, and aquatic plyometric activities. Participants will use assistive devices such as water dumbbells, noodles, inflatable boards, and kickboards so as to engage their entire body in resistance exercise and provide needed support. They will also engage in aerobic activities such as aqua walking or jogging and plyometric activities such as skipping or single leg hopping while in the pool.* After the initial two months, participants may transition to a self-paced program with study staff-led exercise sessions repeated every 2 weeks for the duration of this 4-month phase. *For those veterans who do not wish to transition to a self-paced program, they will continue to attend group-based pool exercise at VAPAHCs. Those veterans who do transition to a self-paced program will have access to the VAPAHCs aquatic facilities during normal "drop-in" hours so that they may continue their thrice-weekly aquatic exercises.* After completion of the exercise-training portion of the intervention, participants will undergo a second series of assessments (i.e., Time 2 assessments). They will then transition to the cognitive training portion of the intervention. The "comprehensive extended" cognitive training program was selected because it has demonstrated efficacy in improvement of delayed recall of the proposed outcome measures (Yesavage et al., 2008). Veterans will participate in 4 weeks of cognitive training before completing the third and final series of assessments (i.e., Time 3 assessments).

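### T2 and T3 are tied to finishing each training phase, no outcome assessment is planned for veterans who stop early, and Aim 1 leaves completion undefined

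*Combined protocol and SAP*

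**What the plan says.** **Timing of assessments.** Under Research Design, Enrollment and Study Implementation, the plan says of T2: "After completion of the exercise training, participants will be re-assessed with the cardiopulmonary exercise testing, cognitive measures, biological measures". Of T3 it says: "At completion of the cognitive training, participants will undergo the post-treatment assessment". The Study Procedures paragraph in the human-subjects part repeats both: "After completion of the exercise-training portion of the intervention, participants will undergo a second series of assessments" and "Veterans will participate in 4 weeks of cognitive training before completing the third and final series of assessments". The Measures paragraph labels the visits "Time 2: End of Exercise Training, Time 3: End of CT", and Data Collection and Database Management uses similar end-of-phase labels. None of these gives weeks from enrolment or a visit window.

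**Veterans who stop.** No section schedules an outcome assessment for them, and none says they will not be assessed. Data Collection and Database Management promises "every effort made to obtain missing data" but names no visit. The only follow-up stated after participation ends early is safety follow-up, under Adverse Events and Serious Adverse Events. Dropouts are not replaced, and the term is not defined as leaving treatment or leaving the study.

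**Analysis.** For Aim 1, "the ratio of enrolled to completed participants will be calculated", with at least 80% counted as good retention. *Completed* is not defined. Aim 3 reports adherence separately. Aim 4 reports the percentage with a clinically relevant change in delayed word-list recall and is described as intent-to-treat with all data analysed.

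**The concern.** Stopping training and becoming untestable are different events. Every participant must have a musculoskeletal condition that makes weight-bearing exercise difficult, while the proposed primary outcome is a word-list recall task. It is plausible that some veterans will give up the pool or the classes and still be able and willing to take the test. If staff follow the written schedule, no test is due for them.

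Two results are then at stake. An intent-to-treat response rate for Aim 4 needs post-treatment scores from people who stopped, and no analysis can recover scores that were never collected. For Aim 1, a larger trial needs to know both how many finish treatment and how many can be measured. A single ratio with an undefined numerator may not tell it either.

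**Working it through.** **Step 1. What is planned for whom.** Reading the two schedule descriptions together with the visit labels:

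| Veteran | T1 | T2 | T3 |
|---|---|---|---|
| Finishes both phases | planned | planned | planned |
| Stops during the classes | planned | planned, already done | not planned |
| Stops during the pool phase | planned | not planned | not planned |

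**Step 2. The plan's own threshold.** Planned enrolment is 50, so 80% is 0.80 × 50 = 40 veterans. As written, enrolled to completed would be 50/40 = 125%; completed over enrolled is evidently meant.

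**Step 3. Two readings of *completed*.** Let S veterans stop treatment, of whom k still attend T3.

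- Treatment completion = (50 − S)/50
- Outcome availability = (50 − S + k)/50
- Gap = k/50

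The documents give neither S nor k for this intervention. With S = 12 assumed:

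| k (assumed) | Treatment completion | Outcome availability |
|---|---|---|
| 0 | 38/50 = 76% | 38/50 = 76% |
| 3 | 76% | 41/50 = 82% |
| 6 | 76% | 44/50 = 88% |
| 9 | 76% | 47/50 = 94% |
| 12 | 76% | 50/50 = 100% |

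For k of 2 or more (38 + 2 = 40), the first reading fails the 80% rule and the second passes.

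**Step 4. When the verdict can change.** If S is 10 or fewer, treatment completion is at least 40/50 = 80%, and both readings pass. The definition can alter the verdict only when at least 11 stop (39/50 = 78%).

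**Step 5. The only loss figure in the documents.** In the team's ongoing trial about 8% were lost to follow-up. Treating that as the rate of stopping here, S = 0.08 × 50 = 4, treatment completion is 46/50 = 92%, and availability lies between 92% and 100%. The gap is at most 4/50 = 8 points, and both readings pass.

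**Step 6. Effect on Aim 4.** Assume about 60% respond among those assessed, and let m veterans lack T3. The lower bound counts the missing as non-responders and the upper bound counts them as responders; the width is m/50.

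| m | Among assessed | Lower bound | Upper bound |
|---|---|---|---|
| 4 | 28/46 = 61% | 28/50 = 56% | 32/50 = 64% |
| 10 | 24/40 = 60% | 24/50 = 48% | 34/50 = 68% |
| 12 | 23/38 = 61% | 23/50 = 46% | 35/50 = 70% |

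Each stopper who is tested narrows the interval by 1/50 = 2 points.

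**The case against.** The strongest reply is that the schedule describes the expected path and excludes nobody. The exercise period has a stated length of about 24 weeks and the classes are given as four weeks, so the end-of-phase labels could be read as calendar time. The plan also promises effort over missing data and calls Aim 4 intent-to-treat, which suggests that outcomes are not meant to be limited to treatment completers. *Completed* may mean attending T3: Study Procedures speaks of completing the final assessments, and payment is per completed assessment set. Aim 3 already reports adherence separately. Finally, losses in the ongoing trial were largely due to acute illness or injury that ended participation. If that recurs, few stoppers could be tested. This is also a single-arm feasibility study with no efficacy comparison.

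Much of this stands, and it limits the point. A reader might infer that a veteran who stops gets no assessment at all, that staff would break off contact, that Aim 1 definitely merges stopping treatment with leaving the study, or that those left unmeasured are the ones least likely to have benefited. The documents support none of these. They are silent rather than prohibitive, they require safety follow-up, a veteran who stops during the classes already has T2, *completed* is undefined rather than wrongly defined, and nothing is said about benefit among stoppers.

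What the reply does not supply is a visit. The calendar reading is possible but not stated, and it is less secure for T3 because the Specific Aims section gives the cognitive training as two weeks. A general promise about missing data sets no date for someone who has left the pool. Adherence under Aim 3 measures sessions and homework, not whether the outcome was obtained.

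**Conclusion.** The point holds in a limited form. The written schedule plans no outcome assessment at a fixed time for a veteran who stops early: T2 and T3 are both unplanned after stopping the pool, and T3 alone after stopping during the classes. This conflicts with the intent-to-treat statement for Aim 4. Because *completed* is undefined, the 80% retention verdict may turn on which meaning is chosen.

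The size is uncertain. The 76% against 88% contrast rests on assumed counts (12 stop, 6 of them attend), and the range for availability is 76% to 100%. The verdict can differ between the two readings only if at least 11 of 50 stop. If stopping resembles the roughly 8% loss in the ongoing trial, the gap is at most 8 points and both readings pass; if most of those losses could not be tested, it is smaller still. The Aim 4 bounds rest on an assumed 60% response. This is a worthwhile, low-cost improvement to the plan, not a flaw that undermines the study.

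**What to change.** 1. **Anchor the visits to time.** In Enrollment and Study Implementation, Measures, Data Collection and Database Management, and Study Procedures, define T2 and T3 by planned time from the first exercise session: T2 at the planned end of the exercise period of about 24 weeks, T3 at the planned end of the cognitive-training period that follows. That period is four weeks in these procedural sections but two weeks in Specific Aims; the two must be reconciled before a date can be set.
2. **Offer the visits to everyone enrolled who has not withdrawn consent**, whether or not sessions continued, with at least the word-list and name-face tasks. Record treatment status for pool and classes at each visit, so that off-treatment scores can be identified. Exercise testing, and whether someone who stopped the pool enters the classes, remain clinical decisions for the study team.
3. **Report two Aim 1 figures**: completed treatment over enrolled, and T3 word-list score obtained over enrolled. State in advance which one the 80% threshold applies to.

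**Cost.** Protocol wording, plus staff time to contact and test the few who stopped. Assessments, with $50 per completed set, are already planned for all 50, but the documents contain no budget, so the absence of added cost cannot be confirmed.

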### **Database Management and Planned Statistical Analyses**

Data Collection and Database Management. There are three proposed testing time points in this study: prior to randomization (T1), at the end of the exercise program and prior to beginning CT (T2), and at the end of the CT (T3). All identifying information will be removed as data are coded by a unique subject number/identifier. Only the PI and her designee will have access to the identifying information linking subject number to name. All data will be checked for completeness and every effort made to obtain missing data. Data storage will be on computerized password protected databases that are backed up nightly. Additionally, our MIRECC and associated laboratories are familiar with the relevant security and confidentiality issues pertaining to genetic materials and take extra safeguards to protect this information.

Data Analyses. Descriptive analyses of categorical variables will include frequency tables; we will compute measures of central tendency (mean, median, standard deviation, and interquartile range) for those continuous variables. Additionally we will examine the distribution of scores on dependent measures to test assumptions of normality and homogeneity of variance and thus make appropriate transformations when necessary.

Specific Aim 1: WATER+CT will be feasible as shown by good recruitment and retention rates. Statistical Analyses: To test feasibility of the proposed project, the ratio of enrolled to completed participants will be calculated;  $\geq 80\%$  will be considered good retention. Specific Aim 2: To evaluate the appropriateness of suggested inclusion and exclusion criteria for the aims of the proposed project. Statistical Analyses: We will examine the reported adverse events for participants as well as reasons for screening failures (i.e., those who are consented but excluded from participation prior to randomization). Descriptive analyses of these data will include frequency tables and be used to provide justification for the proposed inclusion and exclusion criteria or to modify them appropriately. Specific Aim 3: To evaluate appropriateness of the WATER+CT for study goals. Statistical Analyses: Appropriateness of treatment conditions will be determined through examination of the participant adherence data. Adherence data will include information from pedometers, heart rate monitors, 7-day activity logs, and cognitive training homework logs. Adequate adherence to exercise prescriptions and CT homework will be defined as completion of  $\geq 80\%$  of assignments as defined by self-report and trainer observation. Specific Aim 4: To assess outcome measurement techniques for participant rate of response in WATER+CT. Statistical Analyses: As this is a single-arm trial, a direct comparison between the WATER + CT condition and a comparative condition is not possible. Participants response rate will be determined by examining the percentage of participants who evidence clinically relevant change after study participation. To determine what a clinically relevant difference in the primary outcome measure (delayed recall of a Word List) would be, we reanalyzed data from our initial clinical trial (Yesavage et al., 2008). Our strategy was to look in that study at the difference in baseline scores between 60 year olds and 70 year olds on the same measure as the proposed work. We found that the difference was 1.7 words. We believe that showing such a difference would be clinically meaningful insofar as it represents a decade of aging's effects on memory. This will be an intent-to-treat analysis, thus all data will be analyzed. Specific Aim 5: To examine outcome "moderator" and "mediator" measurement techniques to determine: a) in whom and under what conditions clinically relevant change occurs and b) the mechanisms through which clinically relevant change occurs. Here we are referring to within subjects effects. Statistical Analyses: Multiple regression modeling will be performed in a preliminary manner to examine individual differences in treatment response depending on baseline (T1) characteristics (age, level of education, APOE and BDNF genotypes). A significant Response Rate X Moderator interaction indicates a differential response rate, e.g., the response rate depends upon age. Such measures are "moderator" variables, i.e., they are used to determine on whom or under what conditions improvement occurs. Additional analyses will be performed to examine the extent to which individual differences in the efficacy of CT treatments depend upon changes in cardiovascular functioning, BDNF plasma levels, and changes in efficiency of working memory (Digit Span) during combined aerobic and resistance exercise training (T1 to T3). These analyses use changes in these two measures as "mediator" variables, i.e., they are used to determine how or why improvement occurs.

Project Management. To support the Specific Aims stated above, the investigators will perform appropriate tasks within the funding period. The first two months of the funding period (Start-Up Phase) will be devoted to hiring and training of research staff and purchasing activity monitoring devices. The Data Collection Phase will begin in Month 3 and continue through Month 20 to allow adequate time for participants to complete the 8-month long intervention. We will randomize five veterans a month through Month 13. Finally, the Study Close-out Phase will begin in Month 21 with Data Analysis and Manuscript Preparation. These will activities will be completed within Month 24.

**Human Subjects Involvement and Characteristics.** Involvement of human subjects in the proposed study includes participation in a feasibility study of an water-based physical exercise plus cognitive training adjunctive treatment for Mild Cognitive Impairment (MCI) in older veterans. We expect to enroll a total of 50 veterans, age 50 years old to 90, in this study. Using the criteria put forth by Alberts et al (2011), all veterans will be classified as having amnestic MCI. These veterans will be recruited through clinician referral, media advertisement, and local veteran agencies. Participants will also be recruited from the outpatient clinics of the VA Palo Alto Health Care System (VAPAHCS) as well as the Stanford / VA Aging Clinical Research Center (ACRC).

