Few studies have examined the effectiveness of an exercise training program coupled with a memory training program. Given the success of exercise programs with healthy older adults and evidence of some positive effects of in MCI patients, it is important to determine if alternative approaches, such as water-based activity, will extend the benefit for those individuals in whom weight-bearing exercise is not possible. The knowledge gained from this proposal will lay the groundwork for a large-scale clinical trial testing hypotheses about the efficacy of nonpharmacological interventions that target cognitive impairment in persons with MCI. The goal of pilot work is to ascertain that the proposed methods are adequate for a large-scale clinical trial in terms of recruitment and retention of appropriate subjects, inclusion and exclusion criteria, appropriateness of treatment condition, and measures.

The aims listed below will be tested in a two-phase single-arm trial conducted at the VA Palo Alto Health Care System (VAPAHCS) that will include: 1) a physical exercise phase and 2) a cognitive training phase. The six-month exercise phase will consist of non-weight bearing water-based physical exercises. After the six-month exercise phase, veterans will complete a two-week cognitive training program. This two-year proposal will include 50 veterans with MCI aged 50 years to 90.

**Specific Aim 1:** To determine the feasibility of a randomized, controlled trial combining physical activity + cognitive training in persons with MCI as shown by good recruitment and retention rates.

**Specific Aim 2:** To evaluate the appropriateness of suggested inclusion and exclusion criteria for the aims of the proposed project.

**Specific Aim 3:** To evaluate appropriateness of the water-based physical exercise + cognitive training (WATER + CT) conditions for study goals.

**Specific Aim 4:** To assess the ability of selected outcome measurement techniques to determine the efficacy of WATER+CT.

**Specific Aim 5:** To examine outcome "moderator" and "mediator" measurement techniques to determine: a) in whom and under what conditions clinically relevant change occurs and b) the mechanisms through which clinically relevant change occurs.

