Ongoing Study: Exercise Training + Cognitive Training. We have successfully collaborated on the current DOD-funded project, "A Combined Training Program for Veterans with Amnestic Mild Cognitive." This project represents the merging of our interests, namely cognitive training and exercise training, towards a new target problem. At completion in September 2015, this ongoing RCT will compare the effects of a combined aerobic and resistance exercise program + cognitive training (CARE + CT) program to a stretching exercise + cognitive training (SE+ CT) program. Interim results indicate that the intervention is relatively well received by participants, as recruitment and retention rates are positive. To date, fifty-five veterans have been randomized to either the CARE+CT or SE+CT condition. Approximately 8% of those randomized have been lost to follow-up. Reasons for discontinuing study participation were largely due to development of acute illness (i.e., CVA or cancer) or injury (i.e., concussion sustained after fall) that prevented further study participation. There are no group-based differential dropout rates. *The preliminary results of this trial suggest that physical exercise does augment the effect of cognitive training as the CARE+CT group, compared to the SE+CT group, demonstrated clinically significant improvements on measures of learning (CARE+CT group: mean gain score = 13.5, SD=11.21; SE+CT group: mean gain score = 9.5, SD=9.68) and delayed recall (CARE+CT group: mean gain score = 7.25, SD=4.11; SE+CT group: mean gain score = 5.83; SD=2.69).*

Over 1500 veterans have been screened study participation and approximately 15% of those were ineligible due solely to musculoskeletal injuries and illnesses (i.e., impaired gait, osteoporosis, degenerative disc and joint disease) that prevent full engagement in weight-bearing exercises. Given the prevalence of these illnesses and injuries in veterans coupled with the increased risk of cognitive impairment, it is vitally important that we investigate methods to extend the cognitive benefit of physical exercise and cognitive training to all

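### The Aim 1 retention ratio is written the wrong way round, so the 80% criterion cannot fail as stated (minor)

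*Combined protocol and SAP*

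**What the plan says.** Specific Aim 1 is to establish feasibility "as shown by good recruitment and retention rates". The Measures paragraph repeats that feasibility "will be assessed through examination of recruitment and retention rates". Neither place defines a rate.

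The only definition is in the Data Analyses text for Specific Aim 1. There, "the ratio of enrolled to completed participants will be calculated", and a result of 80% or more "will be considered good retention".

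Two further statements fix the range of possible values. Planned enrolment is 50 veterans (Enrollment and Study Implementation; Human Subjects Involvement and Characteristics). The enrolment paragraph also says: "Dropouts will not be replaced as this is a feasibility study".

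**The concern.** A ratio of A to B is A divided by B, so the stated measure puts the number enrolled on top and the number completed underneath. This quantity cannot be less than 1, so a floor of 80% excludes nothing. It also runs in the wrong direction, because more dropout gives a larger value, and a reported figure above 100% could not be read as retention.

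What is at stake is the one explicit threshold attached to the study's first aim. The sections on potential benefit and importance of the knowledge make the follow-on efficacy proposal depend on the project being shown feasible. A rule that supports that judgement should be able to give a negative answer. Sample size, cognitive endpoints and the other analyses do not depend on it.

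**Working it through.** **Inputs**

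- Statistic as written: E / C, where E = enrolled and C = completed (Data Analyses, Specific Aim 1).
- Threshold: at least 80% (same place). This is a chosen cut-off, so there is no computed figure to reproduce.
- E = 50 (Enrollment and Study Implementation; Human Subjects Involvement and Characteristics).
- Dropouts are not replaced (Enrollment and Study Implementation), so C ≤ E.
- Loss in the team's ongoing land-based exercise trial, for illustration only: "Approximately 8% of those randomized have been lost to follow-up" (Preliminary Work; interim).

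**Step 1: the bound.** Since C ≤ E, E / C ≥ 1 for any enrolment and any C of 1 or more. At C = 0 the ratio is undefined.

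**Step 2: values with 50 enrolled**

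| Completed | Enrolled / completed (as written) | Meets 80%? | Completed / enrolled (intended) | Meets 80%? |
|---|---|---|---|---|
| 50 | 100.0% | yes | 100% | yes |
| 46 | 108.7% | yes | 92% | yes |
| 40 | 125.0% | yes | 80% | yes |
| 39 | 128.2% | yes | 78% | no |
| 25 | 200.0% | yes | 50% | no |
| 10 | 500.0% | yes | 20% | no |

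The row for 46 completers corresponds to the 8% loss: 50 × 0.92 = 46.

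**Step 3: when the literal rule would fail.** 50 / C < 0.80 requires C > 50 / 0.80 = 62.5, so at least 63 completers from 50 enrolled, which is impossible. Going through C = 1 to 50 gives no value below 80%.

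**Step 4: where the two readings differ.** C / 50 ≥ 0.80 requires C ≥ 40. The intended rule fails for C = 0 to 39, which is 40 of the 51 possible outcomes. The literal and intended rules give opposite answers for C = 1 to 39.

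**Step 5: whether the corrected rule is workable.** The exact binomial probability of 40 or more completers out of 50 is:

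| True retention | Chance of meeting the corrected rule |
|---|---|
| 60% | 0.2% |
| 70% | 7.9% |
| 80% | 58.4% |
| 90% | 99.1% |
| 92% | 99.8% |

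The corrected rule separates poor from good retention. If the interim loss in the other trial carried over, it would almost certainly be met.

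**Step 6: precision.** Exact (Clopper-Pearson) 95% intervals are 80.8% to 97.8% for 46 of 50, and 66.3% to 90.0% for 40 of 50.

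**The case against.** The best reply is that no one would misread the rule. The sentence names good retention beside an 80% floor, and a retention rate with such a floor has only one sensible meaning, completed over enrolled. On that view this is a copy-edit, and values such as 125% or 200% describe a calculation that nobody will perform. This stands as an argument about severity. It does not make the written rule correct, and no other section supplies the right definition.

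A second reply is that Aim 1 has other numbers: 200 telephone screens, 100 in-office evaluations and about 50 enrolled at 5 per month. The sample size paragraph also links feasibility to recruiting 274 over 5 years at the same rate (274 / 60 months, about 4.6 per month). These are recruitment projections. None is given as a cut-off for what counts as good, and none concerns retention.

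A third reply is that swapping two words cures the error, and that defining completion and the denominator goes further. That is fair. The plan does not say how to count someone who finishes the cognitive training but misses the Time 3 assessment. Those definitions are for the sponsor to confirm. Likewise, the 8% loss comes from a different, unfinished trial and shows only whether the corrected rule is attainable.

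**Conclusion.** The concern holds, and it is minor. As written, the Aim 1 retention criterion is met for every count from 1 to 50 completers and would call 25 of 50 good retention. This follows from completers being a subset of those enrolled. It holds for any enrolment and needs no assumption about alpha, power or effect size. The size of the disagreement with the intended rule (1 to 39 completers) assumes that exactly 50 are enrolled. The probabilities in Step 5 also assume that participants drop out independently with a common probability.

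The error is confined to the wording of one rule. The intended meaning is evident, and no design feature or other analysis is affected.

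**What to change.** In the Data Analyses text for Specific Aim 1, put completed over enrolled and keep the threshold. Suggested wording:

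> Retention is the number of participants who complete the Time 3 assessment divided by the number enrolled after the in-office evaluation. Retention of at least 80% (40 participants if 50 are enrolled) is good. The proportion is reported with an exact 95% confidence interval.

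Reversing the ratio is the correction itself. Three parts of this wording go beyond it:

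- **Completion.** Tying it to Time 3 follows Study Procedures, where Time 3 is the last assessment. The sponsor should confirm this.
- **Denominator.** Counting those enrolled after the in-office evaluation follows Enrollment and Study Implementation, and leaves screening failures to Aim 2. The sponsor should confirm this too, since the Sample size and Project Management paragraphs speak of randomizing participants although the trial has a single arm.
- **Confidence interval.** This is a reporting addition.

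The cost is one sentence, with no change to enrolment, visits, schedule or threshold.
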